### 8.1. MRI Data Processing

Standard and validated tools will be used for image processing. The research team is expert in analyzing brain imaging data and have published several studies focused on MRI-derived blood flow-based measures.

Maps representing gray matter probability and cerebral blood flow will be generated using SPM, FSL, or similar software. Scans will be processed using the most up to date and recommended processing scheme, including methods previously used by our research group and collaborators.

We expect to use standard viewing software (Advanced Workstation 4.3, GE Healthcare) for magnetic resonance angiography and phase contrast data, in addition to

- 1) MIMICS and EnSight, commercial software packages commonly used in 4D flow visualization and
- 2) MatLab-based software for quantitative analysis of 4D data sets

Quantitative data from two 4D multi venc flow acquisitions will be available. The data includes:

- 1) Quantitative blood flow values (peak and mean flow, peak and mean velocity, pulsatility and resistance index) of 4D PC
- 2) Quantitative morphological data (vessel diameter) of:
  - a. Standard magnetic resonance angiography techniques
  - b. 4D PC

### 8.2. Aim 1

Composite scores will be computed by calculating and averaging z-scores within each cognitive domain. Composite total cognitive scores will be predicted from HOMA-IR and the covariates. Pilot data yielded a partial correlation of -0.6 between HOMA-IR and the total cognitive score. A one-tail test of the population correlation coefficient with a Type I error rate of 0.05 requires a sample size of **N=13** to yield power of 0.80. If this composite score test is significant, similar analyses will be performed to examine the relationship between HOMA-IR and individual cognitive ability subdomain scores.

### 8.3. Aim 2

#### 8.3.1. Aim 2 Data Expression

For conceptual clarity, pilot data are expressed as CBF or CP. For statistics, the key dependent variable in Aim 2 is cerebrovascular conductance (CVC), where CVC is CBF or CP normalized to mean arterial pressure (i.e. blood pressure), where

$$\text{CVC} = \text{CBF}/\text{mean arterial pressure}$$

CVC is critical, as:

- 1) it normalizes CBF/CP for differences in mean arterial pressure (up to 15 mmHg across IR spectrum)
- 2) it accounts for mean arterial pressure changes *with* OGTT
- 3) changes in CVC ( $\Delta\text{CVC}$ ) have a predictable relationship *independent* of baseline differences, where  $+\Delta\text{CVC}$  indicates dilation and  $-\Delta\text{CVC}$  indicates constriction (24, 53)

$\text{CVC}_{\text{MACRO}}$  refers to macrocirculation (i.e. CBF) and  $\text{CVC}_{\text{MICRO}}$  to microcirculation (i.e. CP). While  $\text{CVC}_{\text{MACRO}}$  and  $\text{CVC}_{\text{MICRO}}$  are physiologically related, the two levels are conceptually independent. Testing both is crucial as preliminary data indicate resting CBF is normal, yet CP is lower as IR increases.

#### 8.3.2. Aim 2A

Total CVC will be predicted from HOMA-IR and the covariates (intracranial volume is an additional covariate for CVC analyses). Resting CP data indicate reduced perfusion in several anterior brain regions. Pilot data yielded a correlation between HOMA-IR and resting  $\text{CVC}_{\text{MICRO}}$  of  $-0.324$ , such that a sample of size **N=55** will yield the power of 0.8 in a one-tailed test of the correlation, with Type I error rate of 0.05. In contrast, we will test, but do not expect, resting  $\text{CVC}_{\text{MACRO}}$  to be related to HOMA-IR, since resting  $\text{CVC}_{\text{MACRO}}$  is similar in low and high IR.

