## 8. STATISTICAL CONSIDERATIONS

Covariates for all analyses include sex, age, adiposity, aerobic fitness, and education unless noted otherwise.

The overarching statistical approach uses multiple regression to determine whether IR is inversely associated with outcome measures in Aims 1 and 2 and to assess mediation in Aim 3. Mean/summed outcomes (total cognition, total CBF or CP) will be predicted by HOMA-IR, for example. Not only is a composite measure calculated as a mean more reliable than the subdomain scores, but averaging multiple measures of a single construct yields a more powerful hypothesis test than using variables individually (40), under conditions we expect to hold here. This approach avoids inflation of Type I error rate as each hypothesis test examines the relationship among single variables or composites, not among multiple subdomain measures. If the test of the mean or composite score is significant, then there is no increased Type I error rate incurred in subsequent subdomain/regional tests (41).

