Aim 3 tests the mediation effects of CVC on the relationship between HOMA-IR and the composite cognition scores assessed in Aim 1. Mediation will be assessed using the test of joint significance (23). The path between HOMA-IR and perfusion will have been examined in Aim 2. At rest (Aim 3A), mean  $CVC_{MICRO}$  and  $CVC_{MACRO}$  will be examined as the primary mediating variables. Pilot data indicate the correlation between resting  $CVC_{MICRO}$  and cognition is 0.37, so that a sample size of **N=41** would yield 0.8 power in a one-tailed test and Type I error rate of 0.05. During OGTT (Aim 3B), mean peak  $\Delta$ CVC will be the primary mediator variable. Pilot data indicate that the partial correlation between post-OGTT  $\Delta CVC_{MICRO}$  and the total cognitive score was 0.4, so that a directional test of this path requires a sample size of **N=34** to yield the power of 0.8 with Type I error rate of 0.05. A similar power is achieved for  $CVC_{MACRO}$ . If either test (rest or OGTT challenge) is significant, analyses will be performed to examine the mediating effects of CVC between HOMA-IR and individual cognitive ability domain scores.

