#### 8.5. Statistical Summary

With **N=55** for the overall grant, power in Aim 1 increases to near unity, power in Aim 2A is 0.8, power in Aim 2B increases to 0.95, power in Aim 3A increases to 0.9, and that in Aim 3B increases to 0.94, providing this study with sufficient to outstanding power to test the hypotheses of interest.

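### Section 8.5's Aim 3 powers cover only one of the two paths that joint significance requires: Aim 3A is about 0.63 to 0.72, not 0.9, even if the pilot values are partial correlations

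*Combined protocol and SAP*

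**What the plan says.** Section 8.4 (Aim 3) names the mediation test: "Mediation will be assessed using the test of joint significance (23" (the trailing number is a reference). It sends the first path back to the previous aim: "The path between HOMA-IR and perfusion will have been examined in Aim 2". For that path at rest, Section 8.3.2 says that N=55 "will yield the power of 0.8 in a one-tailed test of the correlation, with Type I error rate of 0.05". Section 8.4 then sizes only the perfusion-to-cognition path: N=41 for a correlation of 0.37 at rest (3A), and, for a partial correlation of 0.4 after OGTT (3B), "so that a directional test of this path requires a sample size of" 34.

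Section 8.5 turns these into aim-level powers at N=55: "power in Aim 2A is 0.8, power in Aim 2B increases to 0.95", followed by "power in Aim 3A increases to 0.9, and that in Aim 3B increases to 0.94". It closes by calling the study's power adequate to excellent for its hypotheses.

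On adjustment, Section 8 says "Covariates for all analyses include sex, age, adiposity, aerobic fitness, and education unless noted otherwise", and Section 8.3.2 adds that "intracranial volume is an additional covariate for CVC analyses". That makes five covariates for Aim 1 and six for CVC. The other sizes are N=13 (Aim 1, partial r −0.6), N=55 (2A, r −0.324), N=31 (2B micro, r −0.42) and N=6 (MCA, r −0.796). Sections 8.2 to 8.4 do not name the power formula.

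**The concern.** A joint-significance test succeeds only when both paths are significant, so its power cannot exceed that of the weaker path. For resting mediation the weaker path is Aim 2A, which Section 8.5 puts at 0.8. The 0.9 given for Aim 3A in the same sentence cannot be the power of the planned test.

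The consequence is for interpretation. A reader of a null 3A result would take the chance of missing a true effect of the assumed size to be 10%. On the figures below it is about 28% to 37%, and more if the pilot 0.37 did not hold HOMA-IR constant.

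The stated sizes also make no full allowance for the planned covariates. This shows most plainly where N=6 is given for a test of a partial correlation.

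**Working it through.** **Inputs.** One-tailed alpha 0.05. Correlations and sizes are from Sections 8.2 to 8.4, stated powers from 8.5 and covariates from 8 and 8.3.2, counted as 1 df each. The pilot n is 7 for Aim 1 and 5 for Aims 2 and 3 (Section 3).

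**1. Reproducing the plan.** Use a fixed-predictor noncentral t with λ = √N · r/√(1−r²), df = N−2 and no covariates. The smallest N for power 0.80 is 13, 55, 31, 6, 41 and 34, which matches all six stated sizes. At N=55 the powers are:

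| Aim | r | Computed | Stated |
|---|---|---|---|
| 2A | 0.324 | 0.806 | 0.8 |
| 2B micro | 0.42 | 0.959 | 0.95 |
| 3A, second path | 0.37 | 0.898 | 0.9 |
| 3B, second path | 0.40 | 0.939 | 0.94 |

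So the 0.9 and 0.94 are single-path powers.

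**2. Joint power at N=55 (micro), as the product of the two paths.**

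| Basis | 3A | 3B |
|---|---|---|
| Section 8.5's rounded figures | 0.8 × 0.9 = 0.72 | 0.95 × 0.94 = 0.89 |
| Plan's formula | 0.806 × 0.898 = 0.724 | 0.959 × 0.939 = 0.901 |
| Plan's formula, df cut for covariates | 0.805 × 0.897 = 0.722 | 0.959 × 0.939 = 0.900 |
| Random predictor, covariates counted | 0.746 × 0.840 = 0.627 | 0.923 × 0.891 = 0.823 |

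The random-predictor row treats HOMA-IR as observed, since Section 4.1.1 does not recruit to set IR levels. Exact power with k covariates is then the zero-order power at N−k. Here k=6 for the first path and k=7 for the second (six covariates plus HOMA-IR); using k=6 for the second gives 0.632 and 0.828. Simulating both regressions gave joint powers of about 0.62 and 0.82, so the product is a fair approximation. Joint power of 0.80 for 3A needs N=65 by the plan's formula or N=74 with a random predictor.

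**3. If 0.37 is zero-order.** Section 8.4 calls it a correlation and does not say that HOMA-IR was held constant. Combining it with the plan's −0.6 (HOMA-IR with cognition) and −0.324 (HOMA-IR with resting CVC):

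partial r = (0.37 − 0.6 × 0.324) / √[(1 − 0.36)(1 − 0.105)] = 0.1756 / 0.757 = 0.232.

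Second-path power becomes 0.539 (plan's formula, df cut) or 0.483 (random predictor). Joint power is 0.805 × 0.539 = 0.43 or 0.746 × 0.483 = 0.36. This is illustrative, because −0.6 is itself described as a partial correlation.

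**4. Covariate df.**
- MCA test: intercept, HOMA-IR and six covariates make eight parameters, so N=6 leaves 6 − 8 = −2 residual df.
- Aim 1 at N=13 with five covariates: df = 13 − 7 = 6, and power is 0.77 by the plan's formula.
- Adjusted minimum sizes for MCA and Aim 1 are 10 and 14 (plan's formula, df cut), or 14 and 20 (random predictor).
- At N=55 both tests have power above 0.99.

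**5. Aim 2A.** Unadjusted, 0.806; df cut for six covariates, 0.805; random predictor with partial r 0.324, 0.746.

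**6. Pilot basis.** With n=7, adjusting for all five covariates leaves 7 − 2 − 5 = 0 df. The pilot partial correlations therefore cannot reflect the full planned model, and the text does not say what they adjust for.

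**The case against.** Section 8.4 is open about method: it says the first path belongs to Aim 2 and describes the 3B size as a test of one path. A careful reader could assemble the joint power. That stands for 8.4 but not for 8.5, which presents the single-path figures as the power of Aims 3A and 3B.

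N=6 and N=13 do not drive the design, and Aim 1's near-certain power at N=55 is correct. That stands, so this part is secondary.

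A reader might infer that Aim 2A's 0.8, and so N=55 itself, is an arithmetic error. The documents do not support this. Section 8.3.2 claims 0.8 for an unadjusted correlation, which is right, and the figure stays at 0.805 after a df-only adjustment. The drop to about 0.75 needs both a random predictor and a partial r equal to 0.324. Power conditional on the predictors is a standard basis, and the documents give no covariate R², so the true adjusted power could lie on either side.

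A reader might also infer that adjustment was ignored throughout. That goes too far. Some effect sizes are called partial, 55, 31 and 41 survive the df cut, and 13 and 34 also reproduce with one or two covariates. Only N=6 requires none.

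**Conclusion.** The stated power for Aim 3A is wrong for the planned test. It cannot exceed 0.8, and is about 0.72 on the plan's own figures and about 0.63 with a random predictor and covariates counted, against a stated 0.9. Aim 3B is about 0.82 to 0.90 against 0.94, so it still clears 0.80. Both ranges treat the paths as independent and assume that the pilot values are the true partial correlations with HOMA-IR held constant. If 0.37 is zero-order, 3A is nearer 0.36 to 0.43, so 0.63 is not a lower bound.

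Secondary: N=6 is impossible and N=13 slightly too small for the adjusted tests, with no effect on the study size. Aim 2A is a caveat (about 0.75 to 0.80 by convention), not an error. The documents do not support a conclusion that the study as a whole is underpowered.

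**What to change.** Keep N=55 and revise the wording of Sections 8.2 to 8.5:

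- Label 0.9 and 0.94 as powers of the perfusion-to-cognition path. Add joint-significance powers of about 0.63 to 0.72 for 3A and 0.82 to 0.90 for 3B, stating that they assume partial correlations with HOMA-IR held constant.
- Withdraw the closing claim of adequate-to-excellent power for resting mediation.
- Delete N=6 and N=13, or replace them with adjusted sizes: 10 and 14 by the plan's formula with the df cut, or 14 and 20 with a random predictor.
- Name the power formula and give 2A as 0.75 to 0.80 depending on convention.
- For each pilot correlation, state the n, the covariates used and whether HOMA-IR was held constant.

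The cost is protocol text only; no procedure, analysis or sample size changes. Section 8.5 could no longer imply at least 0.80 power for every aim.

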#### 8.3.3. Aim 2B

The change in CVC ( $\Delta\text{CVC}$ ) will be predicted from HOMA-IR and the covariates, where

$$\Delta\text{CVC} = (\text{peak CVC during OGTT}) - (\text{resting CVC})$$

Pilot data indicate the average correlation between HOMA-IR and  $\Delta\text{CVC}_{\text{MICRO}}$  of  $-0.42$ , so a one-tailed test of the partial correlation will yield power of 0.80 with a sample size of **N=31**, with Type I error rate of 0.05. We plan to assess numerous regions of interest (ROIs) linked to executive functions and memory, including frontal, temporal, and parietal regions (e.g. middle, medial, and superior frontal gyri, anterior cingulate, hippocampus, middle and superior temporal gyri, posterior cingulate, precuneus), as well as ROIs *with less involvement* in memory or executive functions (e.g. precentral and postcentral gyri, occipital cortex).  $\Delta\text{CVC}_{\text{MICRO}}$  is only predicted from HOMA-IR within an ROI, not between, to limit the number of comparisons and therefore limit the false discovery rate.

For  $\Delta\text{CVC}_{\text{MACRO}}$ , up to 11 extra- and intra cranial arteries will be studied (basilar, 2 ACA, 2 MCA, 2 PCA, 2 vertebral, and 2 ICA; dependent on individual anatomy). Total CBF will be calculated, where

$$\text{CBF}_{\text{TOTAL}} = \text{CBF}_{\text{BASILAR}} + \text{CBF}_{\text{ICA-Right}} + \text{CBF}_{\text{ICA-Left}}$$

Pilot data indicate that the average correlation between HOMA-IR and MCA perfusion during OGTT is -0.796, so that a one-tailed test of the partial correlation will yield the power of 0.80 with a sample size N=6, with Type I error rate of 0.05. For all of Aim 2, if either total CVC test is significant (micro or macro), similar regression analyses will be performed to examine the mediating effects of  $\Delta$ CVC between HOMA-IR and individual ROI (micro) or artery (macro)  $\Delta$ CVC values.

#### 8.4. Aim 3

Aim 3 tests the mediation effects of CVC on the relationship between HOMA-IR and the composite cognition scores assessed in Aim 1. Mediation will be assessed using the test of joint significance (23). The path between HOMA-IR and perfusion will have been examined in Aim 2. At rest (Aim 3A), mean  $CVC_{MICRO}$  and  $CVC_{MACRO}$  will be examined as the primary mediating variables. Pilot data indicate the correlation between resting  $CVC_{MICRO}$  and cognition is 0.37, so that a sample size of **N=41** would yield 0.8 power in a one-tailed test and Type I error rate of 0.05. During OGTT (Aim 3B), mean peak  $\Delta$ CVC will be the primary mediator variable. Pilot data indicate that the partial correlation between post-OGTT  $\Delta CVC_{MICRO}$  and the total cognitive score was 0.4, so that a directional test of this path requires a sample size of **N=34** to yield the power of 0.8 with Type I error rate of 0.05. A similar power is achieved for  $CVC_{MACRO}$ . If either test (rest or OGTT challenge) is significant, analyses will be performed to examine the mediating effects of CVC between HOMA-IR and individual cognitive ability domain scores.

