##### 3.1.2. Preliminary Data

Pilot data indicate similar brain and hippocampal volumes between groups (2.93 vs 2.84 mm^3). Cognitive testing results did not differ significantly between groups. However, episodic memory, executive function, and attention, as well as total composite cognition scores were all quantitatively lower in adolescents with high IR. Notably, these smoldering decreases in cognition are directly correlated to HOMA-IR. Collectively, these data suggest brain structure remains intact at this stage, yet fundamental memory and attention measures are declining in relation to worsening insulin resistance.

#### 3.2. Aim 2

To test the hypothesis that adolescents with higher IR:

- a) exhibit intact resting global macrovascular CBF but reduced microvascular perfusion in key brain areas involved in cognition, memory, and learning
- b) will exhibit further perfusion reductions in response to an endogenous insulin surge in contrast to increased perfusion in healthy adolescents.

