### 3.2.2. Preliminary Data

First, total CBF is remarkably similar between groups (PC VIPR). However, adolescents with high IR exhibit reduced basal microvascular CP in numerous brain regions, including those involved in cognitive processing (ASL). The combination of MRI approaches suggests an uncoupling of macro and microvascular flow (17) (34), consistent with early but subtle *basal* microvascular dysfunction in IR. Therefore, it is crucial to look at both CBF and CP measures, as regional regulation appears to be differently affected by IR.

Second, following OGTT, regional CBF and CP patterns change markedly. Despite similar increases in plasma glucose, insulin increases much more in adolescents with high IR. CBF through the Middle Cerebral Artery (MCA) increases in adolescents with low IR but *decreases* in adolescents with high IR. Similar patterns were observed in the Anterior Cerebral Artery (ACA, not shown). Third, 45 minutes into OGTT, select regions increased CP in adolescents with low IR, but *decreased* CP in adolescents with high IR. Notably, many of these regions are downstream of the MCA and ACA and are linked with executive function, memory, and learning abilities. These data strongly support the hypothesis that adolescents with high IR demonstrate overt brain endothelial dysfunction, which decreases brain perfusion under the physiologic stress of hyperinsulinemia and hyperglycemia.

In summary, the combination of PC VIPR and ASL MRI approaches allow us to quantify dynamic CBF/CP responses, identify brain regions most sensitive to insulin vasodilation, and most impacted by IR. Preliminary data for Aim 2 OGTT evokes hypoperfusion occurring primarily in anterior brain regions associated with executive function and memory. In the context of insulin-driven ROS production (20, 21), and lower cognition scores (Aim 1), these data are consistent with the hypothesis that acute brain hypoperfusion, via daily insulin surges, plays an essential role in the early pathology of cognitive dysfunction in adolescents with high IR.

## 3.3. Aim 3

To test the hypothesis that higher IR is associated with lower cognitive function (Aim 1) in such a way that perfusion at rest (Aim 2A), and perfusion changes during insulin surge in particular (Aim 2B), mediate the relationship.

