#### 4.3.3.c. OGTT and MRI Scanning Visit

Duration: Approximately 2 hours.

Subjects will arrive fasted.

Subjects will have one (1) IV catheter placed (see section [4.3.4.i. Intravenous Catheter](#) for details) and then lie supine in the MRI machine. Subjects undergo baseline MRI scans lasting approximately 20 minutes, following which subjects will be removed from the MRI bore to sit to drink 75g glucose (OGTT; see section [4.3.4.g. Oral Glucose Tolerance Test \(OGTT\)](#) for details) within 5 minutes followed by return to MRI bore. Finally, paired MRI scans (PC VIPR and ASL) will be repeated over the next 60 min, with IV blood sampling to quantify insulin and glucose changes. MRI scan time will end approximately 60 min post-OGTT:

[figure not shown]
- 1) for subject comfort in MRI
- 2) as pilot studies indicate robust perfusion changes occur within 60 minutes

ASL scans will be taken at the following time points (note times are approximate due to variance in scan times):

- Baseline (pre-OGTT)
- 10 minutes after OGTT
- 25 minutes after OGTT
- 40 minutes after OGTT
- 55 minutes after OGTT

PC VIPR scans will be taken at the following time points (note times are approximate due to variance in scan times):

- Baseline (pre-OGTT)
- 15 minutes after OGTT
- 30 minutes after OGTT
- 45 minutes after OGTT
- 60 minutes after OGTT

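### Read as written, the Aim 2B change score takes the highest post-glucose scan, so it can report a real fall in perfusion as dilation

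*Combined protocol and SAP*

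**What the plan says.** Section 8.3.3 sets the Aim 2B outcome as ΔCVC, equal to "peak CVC during OGTT" minus resting CVC, and regresses it on HOMA-IR and the covariates. No section gives a rule for the peak. The peak and mean flow listed in 8.1 are outputs of the 4D flow software, not a definition of this variable.

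Section 8.4 carries the term into Aim 3B ("During OGTT (Aim 3B), mean peak" ΔCVC) as the primary mediator.

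Three other places bear on the meaning:

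- Section 8.3.1 gives the sign a physiological meaning: positive ΔCVC is dilation, negative is constriction.
- Section 3.2 (Aim 2b) predicts that adolescents with higher IR "will exhibit further perfusion reductions in response to an endogenous insulin surge in contrast to increased perfusion in healthy adolescents".
- Section 3.2.2 reports pilot rises in low IR and falls in high IR, with the regional result given at one time ("Third, 45 minutes into OGTT, select regions increased CP in adolescents with low IR").

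Section 4.3.3.c schedules one baseline and four post-glucose scans per method. The last ASL scan is "55 minutes after OGTT" and the last PC VIPR scan is at 60 minutes. Section 10 accepts three of five ASL scans. If baseline is one of the three, a subject contributes two to four post-glucose scans.

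**The concern.** The highest of several noisy readings lies at or above any single reading and above their average. A rule that picks it leans toward dilation, while Aim 2b predicts a fall in the subjects of most interest.

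Two things are at stake. First, the sign of ΔCVC can no longer carry the meaning that 8.3.1 gives it: a subject whose perfusion truly falls at some scans can be recorded as dilating. Second, when the response appears at only some scans, the maximum is drawn from the scans where a falling subject has not fallen, which flattens the slope on HOMA-IR. The same variable feeds Aim 2B and the Aim 3B mediator. Because the context points to another reading than the formula, the choice could also be made after the data are seen.

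**Working it through.** **The plan's own figure.** Section 8.3.3 gives r = −0.42, one-tailed α = 0.05, power 0.80, N = 31. By Fisher's z, ((1.645 + 0.842)/atanh 0.42)² = 30.85, which rounds up to 31. At N = 55 the same formula gives power 0.953, matching the 0.95 in 8.5. (The usual formula adds 3, giving 34, and power 0.94 at N = 55; that is a side matter.) So the stated figures reproduce. They say nothing about how the peak is chosen.

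**Assumptions for the rest.** The documents give no scan noise and no time course. I assume normal noise of equal SD on every scan, baseline included, and work in scan SD units. Noise is independent between scans unless stated.

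**Level, no true change, literal rule.** With k post-glucose scans, ΔCVC = max(e₁,…,e_k) − e₀.

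- The expected value is the mean of the largest of k standard normals: 1/√π = 0.56 for k = 2, 3/(2√π) = 0.85 for k = 3, and 1.03 for k = 4.
- ΔCVC is negative only if baseline is the highest of k + 1 exchangeable readings, so with probability 1/(k + 1): 33%, 25%, 20%.
- With serial noise correlation of 0.7 the shifts are +0.31, +0.51, +0.66, and 36%, 29%, 24% of subjects are negative.
- The mean change and the largest signed change both have expectation 0 and are negative in 50%, by symmetry.

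**Level, true fall.**

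- A 1 SD fall at all four scans: 1.03 − 1.00 = +0.03, with 51% of subjects positive. At one fixed scan it is −1.00, with 24% positive.
- A 2 SD fall at the last two of four scans: the maximum gives +0.58, with 33% negative. The mean gives (0 + 0 − 2 − 2)/4 = −1.00; its SD is √(1/4 + 1) = 1.118, so Φ(1/1.118) = 81% are negative. The largest signed change gives −1.97, also about 81% negative.

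**Slope on HOMA-IR.** If a subject's response A is the same at every scan, max(A + e_j) − e₀ = A + max(e_j) − e₀. The selection adds the same expected amount to everyone, which goes into the intercept, and the slope is unchanged.

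**Power at N = 55, one-tailed 0.05.** Simulated with simple regression on standardised HOMA-IR. Response amplitude = average response − 0.7 × HOMA-IR + between-subject SD 0.8; scan SD 1. The late ramp has weights 0, 0.5, 1, 1; the brief response is one randomly timed scan per subject.

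| Response | Average response (SD) | Maximum | Mean | Largest signed |
|---|---|---|---|---|
| Sustained | – | 0.96 | 0.97 | 0.95 |
| Late ramp | −1 | 0.47 | 0.82 | 0.78 |
| Late ramp | 0 | 0.73 | 0.82 | 0.78 |
| Late ramp | +1 | 0.88 | 0.82 | 0.79 |
| Brief | −1 | 0.14 | 0.30 | 0.44 |
| Brief | 0 | 0.33 | 0.30 | 0.38 |
| Brief | +1 | 0.64 | 0.30 | 0.45 |

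These depend on the signal-to-noise ratio. With between-subject SD 1.4 and scan SD 0.3, a brief response at average −1 gives 0.55 / 0.82 / 0.94 (maximum / mean / largest signed), and a late ramp at +1 gives 0.94 / 0.95 / 0.95.

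**The case against.** The strongest reply is that the literal reading was never meant. In 8.4 the word peak qualifies ΔCVC, that is, the change and not the level. ΔCVC is signed, and the pilot reports decreases. All this fits the largest change in either direction, under which the one-way shift disappears. That stands as evidence of intent, but the formula in 8.3.3 still says something else. The pilot does not settle it: two of the sizing correlations are described as "the average correlation between HOMA-IR and MCA perfusion during OGTT is -0.796" and, in 8.4, "Pilot data indicate that the partial correlation between post-OGTT" ΔCVC, with no selection rule.

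It is also fair that no planned test uses the sign of an individual's ΔCVC, and that −0.42 and 0.4 are reported for ΔCVC itself. If the pilot used the written formula, those values already contain any attenuation, and the stated power needs no correction on this account.

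Four stronger readings are tempting, and the documents do not support them:

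- *The Aim 2B test is biased.* It is a slope on HOMA-IR, and a uniform shift leaves it alone.
- *Power is lost in general.* The largest losses need an average fall across the cohort. Aim 2b and the pilot describe a crossover, closer to an average of zero, where the table shows 0.73 against 0.82 for the mean (late ramp) and 0.33 against 0.30 (brief). Nor is the maximum always better when the average is a rise.
- *False positives are inflated.* That requires scan completion to depend on IR. Nothing in the documents shows this, and section 10 re-invites subjects whose data fall below the validity minimum.
- *The mean in the Aim 3B mediator is unexplained.* The opening of section 8 tests mean or summed outcomes, and Aim 3A is worded in parallel, so it is most naturally the composite over regions or vessels. Only the order of averaging and selecting is open.

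**Conclusion.** The concern holds as a conflict between a stated formula and the plan's own interpretation and hypothesis. Taken literally, 8.3.3 makes ΔCVC negative only when all completed post-glucose scans are below rest. Under independent equal noise that shifts an unchanged subject by +0.56 to +1.03 scan SD (two to four scans), and by +0.31 to +0.66 if serial correlation is 0.7. A fall confined to the later scans can come out as a rise.

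The consequence that does not depend on the time course is for statements about dilation or constriction drawn from the sign or size of ΔCVC. The consequence for the HOMA-IR test is conditional: almost none for a sustained response, a possibly large power loss for a partial response whose average is a fall, and none or even a gain in other cases. Noise, correlation and time course are all assumptions. The matter is worth settling before analysis because one definition governs both Aim 2B and Aim 3B.

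**What to change.** In 8.3.3, before analysis, replace the formula with: *ΔCVC is the change from the baseline scan, among completed post-glucose scans, that is largest in absolute value, keeping its sign.* State that it is taken on the total or composite CVC for the primary test, and within each ROI or artery for the follow-up tests; this also settles the order of averaging. In 8.4, name the same variable as the Aim 3B mediator. Report the mean change over completed post-glucose scans as a sensitivity analysis.

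The cost is wording only; the scans do not change. The largest signed change still depends somewhat on how many scans were completed, and may have slightly less power than the mean for sustained or ramped responses (0.95 against 0.97, and 0.78 against 0.82, under the first set of assumptions). If the pilot used a different definition, the −0.42 and 0.4 sizing correlations should be recomputed on the new one.
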